8.4.1 Additional Analyses of the Secondary Efficacy Endpoint

The analysis of the secondary endpoint will be repeated based on the MMIAS.

A large rectangular area of the page is completely blacked out, indicating that the content has been redacted for confidentiality.

[figure not shown]

Elezanumab (ABT-555)
M19-148 – Statistical Analysis Plan
Version 3.0 – 08 May 2024

[figure not shown]

Elezanumab (ABT-555)
M19-148 – Statistical Analysis Plan
Version 3.0 – 08 May 2024

[figure not shown]

Elezanumab (ABT-555)
M19-148 – Statistical Analysis Plan
Version 3.0 – 08 May 2024

[figure not shown]

Elezanumab (ABT-555)
M19-148 – Statistical Analysis Plan
Version 3.0 – 08 May 2024

Elezanumab (ABT-555)
M19-148 – Statistical Analysis Plan
Version 3.0 – 08 May 2024

8.6 Efficacy Subgroup Analyses

Subgroup analysis of the change from baseline in NIHSS total score will be conducted for the following subgroups at Day 2-4, Week 4, Week 12, Week 24, and Week 52:

- Age (< 70, 70 - < 80, \geq 80 years at time of randomization)
- Sex (male, female)
- NIHSS total score at baseline (< 15, \geq 15)
- Time since last known normal based on actual study drug initiation time (\leq 12 hours, > 12 hours)
- tPA use (Yes, No)
- EVT use (Yes, No)
- Either tPA +/- EVT use (Yes, No)

This will be based on an ANCOVA as observed, with change from baseline as the dependent variable and including treatment and the stratification factors (except for the subgroup analysis corresponding to that stratification term, in which case that particular term will not be included in the model) as main effects and baseline NIHSS as a covariate. This will be based on the subsets for each subgroup separately, at the following time points: Day 2-4, Week 4, Week 12, Week 24, Week 52.

The number and percentage of responders based on the modified Rankin Scale (mRS 0-2) will be repeated for the subsets above using a non-responder imputation at Week 4, Week 12, Week 24, Week 52. The difference between treatment groups and corresponding 95% CI for the difference based on the Wald method will be produced.

A forest plot of each of the subgroups will be presented for each analysis at the time points Week 4, Week 12, Week 24, Week 52 based on the same outputs used in the tables.

8.7 Biomarker Analyses

Biomarker variables neurofilament light (NFL), glial fibrillary acidic protein (GFAP), interleukin 6 (IL6) and repulsive guidance molecule a (RGMa) will be summarized for all

time points (starting with Baseline) with the number of non-missing observations, mean and standard deviation, median, minimum, and maximum. Mean change from baseline to each applicable post-baseline visit will be summarized as observed. The within-group and between-group LS means, SE, and 95% confidence intervals will be presented based on an ANCOVA with baseline as a covariate and treatment as a main effect.

9.0 Safety Analyses

9.1 General Considerations

Safety data will be summarized for the Safety Analysis Set as described in Section [4.0](#). Safety summaries will be presented by treatment group.

"Baseline" refers to the last non-missing observation before the first administration of study drug.

9.2 Adverse Events

Adverse events (AEs) will be summarized and presented using primary MedDRA SOCs and preferred terms (PTs) according to the version of the MedDRA coding dictionary used for the study at the time of database lock. The actual version of the MedDRA coding dictionary used will be noted in the AE tables and in the clinical study report. Specific adverse events will be counted once for each subject for calculating percentages, unless stated otherwise. In addition, if the same adverse event occurs multiple times within a subject, the highest severity and level of relationship to investigational product will be reported.

9.2.1 Treatment-Emergent Adverse Events

Treatment-emergent AEs are defined as any AE with the onset that is on or after the first dose date. Events where the onset date is the same as the study drug start date are assumed to be treatment-emergent. All treatment-emergent AEs will be summarized overall, as well as by primary MedDRA SOC and Preferred Term. The SOCs will be presented in alphabetical order, and the PTs will be presented in alphabetical order within each SOC.

The number and percentage of subjects experiencing treatment-emergent AEs will be summarized.

9.2.2 Adverse Event Overview

An overview of AEs will be presented consisting of the number and percentage of subjects experiencing at least one event for each of the following AE categories:

- Any treatment-emergent AE
- Any treatment-emergent AE related to study drug according to the investigator
- Any severe treatment-emergent AE
- Any serious treatment-emergent AE
- Any serious treatment-emergent AE related to study drug according to the investigator
- Any treatment-emergent AE leading to discontinuation of study drug
- Any treatment-emergent AE leading to death
- Any treatment-emergent AE of special interest
- All deaths

An overview of treatment-emergent AEs of special interest will also be presented, including the above categories and for each of the AESI SMQ/CMQs noted in [Appendix B](#).

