4 INVESTIGATIONAL PLAN

4.1 Overall Study Design and Plan

This is a 52-week, Phase 2a, randomized, double-blind, parallel-group, placebo-controlled, multicenter proof-of concept study to evaluate the safety and efficacy of elezanumab in subjects with acute ischemic stroke.

The schematic of the study is shown in [Figure 1](#). Further details regarding study procedures are located in the Operations Manual ([Appendix F](#)). Also see Section 5 for information regarding eligibility criteria.

The Screening Period is up to 24 hours since "last known normal" (the time before hospital arrival at which the subject was last known to be without the signs and symptoms of the current stroke or at his or her baseline state of health). Treatment with IV tPA and/or EVT will be allowed before randomization and will be recorded as a concomitant therapy.

[figure not shown]
Randomization will be stratified by IV tPA use (yes/no), by EVT use (yes/no), and by time since last known normal (≤ 11 hours or > 11 hours). The proportion of subjects enrolled who have EVT is targeted to be up to approximately 50% of the study population. A target of approximately 25% to 50% of subjects may be randomized within the time window of ≤ 11 hours since last known normal. Lastly, the proportion of subjects who enroll > 80 to 90 years of age is targeted to be up to approximately 30% of the study population. Eligible subjects will be randomized in a 1:1 ratio to receive either elezanumab 1800 mg or placebo as an IV infusion.

Administration of blinded study drug must be initiated as soon as possible but no later than 6 hours after randomization and done every 4 weeks thereafter through Week 48 for a total of 13 doses. The final double-blind Treatment Period study visit will be at Week 52. Subjects will have 2 post-treatment follow-up visits at 12 and 24 weeks after last dose of study drug, and a final follow-up phone call 39 weeks (5 half-lives) after last dose of study drug. All follow-up visits beginning at Week 4 during the Treatment Period and Follow-up Period will be allowed a window of \pm 7 days, and study procedures may be conducted over a period of 2 days. Unblinded safety data will be reviewed by an external DMC per the DMC Charter.

Final efficacy analyses will be performed after the last subject completes the Week 52 visit. Final safety analyses will be performed following completion of the post-treatment period and database lock.

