5.6 Follow-Up for Subject Withdrawal from Study

Study Drug Discontinuation

For subjects who discontinue the study drug, all efforts should be made to continue conducting all treatment and post-treatment procedures (with the exception of study drug administration) in accordance with the study visit schedule and the subject's continued willingness to participate in order to minimize missing data for efficacy and safety assessments. If a subject discontinued study drug and is unwilling to return to the site, certain assessments may be conducted remotely. At a minimum, subjects should complete the procedures outlined for the Week 52/Premature Discontinuation visit (PD visit), and follow-up visits at 12 and 24 weeks after last dose of study drug. Subjects should be advised on the continued scientific importance of their data even if they discontinue treatment with study drug early.

Withdrawal from the Study

In the event that a subject withdraws or is discontinued from the study, the primary reason for discontinuation and any other reason(s) for discontinuation from the study will be recorded on the appropriate eCRF page. If a subject prematurely discontinues study participation, the procedures outlined for the Week 52/PD visit should be completed as soon as possible, preferably within 2 weeks. In addition, a follow-up phone call 30 days after the last dose of study drug should be attempted to ensure all treatment-emergent AEs/SAEs have been resolved.

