An important medical event that may not be immediately life-threatening or result in death or hospitalization, but based on medical judgment may jeopardize the subject and may require medical or surgical intervention to prevent any of the outcomes listed above (i.e., death of subject, life threatening, hospitalization, prolongation of hospitalization, congenital anomaly, or persistent or significant disability/incapacity). Additionally, any elective or spontaneous abortion or stillbirth is considered an important medical event.

All AEs reported from the time of study drug administration until 39 weeks (5 half-lives) after discontinuation of study drug administration will be collected, whether solicited or spontaneously reported by the subject. In addition, study procedure-related serious and nonserious AEs will be collected from the time the subject signs the study-specific informed consent.

The following definitions will be used for Serious Adverse Reactions (SAR) and Suspected Unexpected Serious Adverse Reactions (SUSAR):

SAR	Defined as all noxious and unintended responses to an Investigational Medicinal Product (IMP) related to any dose administered that result in an SAE as defined above
SUSAR	Refers to individual SAE case reports from clinical trials where a causal relationship between the SAE and the IMP was suspected by either the sponsor or the investigator, is unexpected (not listed in the applicable Reference Safety Information), and meets one of the above serious criteria.

AbbVie will be responsible for SUSAR reporting for the IMP in accordance with global and local requirements.

Adverse events will be monitored throughout the study to identify any of special interest that may indicate a trend or risk to subjects.

Adverse Event Severity and Relationship to Study Drug

The investigators will rate the severity of each AE as mild, moderate, or severe.

The investigator will use the following definitions to rate the severity of each AE:

Mild	The adverse event is transient and easily tolerated by the subject.
Moderate	The adverse event causes the subject discomfort and interrupts the subject's usual activities.
Severe	The adverse event causes considerable interference with the subject's usual activities and may be incapacitating or life threatening.

The investigator will use the following definitions to assess the relationship of the AE to the use of study drug:

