7.3 Prior and Concomitant Medications

The number and percentage of subjects taking prior and concomitant medications will be summarized separately by generic name based on the World Health Organization (WHO) Drug Dictionary. A prior medication is defined as any medication taken prior to the date of the study drug initiation. A concomitant medication is defined as any medication that started prior to the date of study drug initiation and continued to be taken after study drug initiation or any medication that started on or after the date of study drug initiation, but not after the date of the last dose of study drug plus 39 weeks (273 days).

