9.2.3 Treatment-Emergent Adverse Events by SOC and PT

Treatment-emergent adverse events and corresponding subject numbers will be summarized by SOC and PT; by maximum relationship to study drug as assessed by the investigator (e.g., reasonable possibility or no reasonable possibility) and SOC and PT; by maximum severity and SOC and PT; and by subject number and SOC and PT. Specific adverse events will be counted once for each subject for calculating percentages, unless stated otherwise. In addition, if the same adverse event occurs multiple times within a subject, the highest severity and level of relationship to investigational product will be reported.

In addition, treatment-emergent adverse events will be summarized by PT and sorted by decreasing frequency for the elezanumab group.

Recurrent stroke events based on the embolic and thrombotic events SMQ provided in [Appendix B](#) will be tabulated and listed.

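### The adverse-event window moves with the last dose (about Week 39 to Week 87), yet the SAP tabulates only crude percentages, so unequal early stopping would understate later events in the arm that stops more

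*SAP*

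**What the plan says.** **Collection rule.** Protocol 6.1: "All AEs reported from the time of study drug administration until 39 weeks (5 half-lives) after discontinuation of study drug administration will be collected".

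**Dosing and last contact.** Protocol 4.1 gives study drug "every 4 weeks thereafter through Week 48 for a total of 13 doses" and plans "a final follow-up phone call 39 weeks (5 half-lives) after last dose of study drug". SAP 7.3 uses the same interval for concomitant medication, ending at "the date of the last dose of study drug plus 39 weeks (273 days" days).

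**What is counted.** SAP 9.2.1: "Treatment-emergent AEs are defined as any AE with the onset that is on or after the first dose date". No end date is given.

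**How it is reported.** SAP 9.2.2: "An overview of AEs will be presented consisting of the number and percentage of subjects experiencing at least one event". SAP 9.2.3: "Specific adverse events will be counted once for each subject for calculating percentages, unless stated otherwise". SAP 9.2.4 summarises serious events and events leading to discontinuation by system organ class and preferred term. The visible SAP section 9 contains no person-time rate, time-to-event summary or fixed-window percentage. SAP section 6.0 reports treatment duration (last dose minus first dose plus 28 days). That is neither the adverse-event observation time nor a denominator for the event tables.

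**After stopping drug.** For a subject who stops drug but stays in the study, Protocol 5.6 says "all efforts should be made to continue conducting all treatment and post-treatment procedures". For a subject who leaves the study, it asks for the premature-discontinuation visit and an attempted phone call 30 days after the last dose.

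**Monitoring period.** Protocol 3.4 and SAP 3.4 list adverse-event monitoring among evaluations covering the whole study, and Protocol 6.1 also has investigators monitor throughout.

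**The concern.** Length of observation depends on something that happens after randomisation: when dosing stops. A crude percentage then mixes the risk of an event with the time during which it could be recorded. If one arm stops more, its percentages for events that keep accruing are lowered for a reason unrelated to the drug.

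Safety is a stated objective and the tables are shown side by side by arm. The exposure is therefore a muted safety signal, or an apparent advantage that is not real.

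A second issue is that the documents disagree on whether events found at visits attended after the 39-week limit are to be recorded.

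**Working it through.** **1. The plan's own figures.** Doses: 48/4 + 1 = 13, as stated. 39 weeks × 7 = 273 days, as stated in SAP 7.3.

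**2. Window.** End of collection = last-dose week + 39, taking discontinuation as the last dose. For last doses at Weeks 0, 4, 8, …, 48 this gives Weeks 39, 43, 47, …, 87. The ratio of longest to shortest is 87/39 = 2.2.

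**3. Identical constant hazards.** The mortality and discontinuation rates in SAP 2.4 are redacted, so stopping shares are assumptions: 35% v 15%, spread evenly over last doses at Weeks 0, 4, …, 24, with everyone else completing. For 87-week risk R, λ = −ln(1−R)/87 and F(t) = 1 − exp(−λt).

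- R = 30%: λ = 0.0041 per week. Risks for the seven early windows (39 to 63 weeks) are 14.8, 16.2, 17.5, 18.9, 20.2, 21.5 and 22.8%, mean 18.8%.
- Arm with 35% stopping: 0.65 × 30 + 0.35 × 18.8 = 26.1%.
- Arm with 15% stopping: 0.85 × 30 + 0.15 × 18.8 = 28.3%.
- R = 60%, same method: 53.5% v 57.2%.

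**4. If every early stopper is followed to at least Week 52.** Each window becomes max(last-dose week + 39, 52). R = 30% gives 26.6% v 28.5%; R = 60% gives 54.4% v 57.6%. The gap shrinks slightly but does not close.

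**5. Front-loaded hazard, identical in both arms.** Assume 70% of the cumulative hazard falls evenly in Weeks 0 to 12 and 30% evenly in Weeks 12 to 87. Shares and R = 30% are as in step 3.

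| Summary | 35% stopping | 15% stopping |
|---|---|---|
| Crude percentage | 28.7% | 29.4% |
| First events per 100 patient-years | 26.3 | 24.7 |
| Percentage in first 39 weeks | 25.0% | 25.0% |

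The rate is events divided by time to first event or end of window: 0.2871/56.97 weeks and 0.2945/62.15 weeks, each × 5218 (52.18 weeks per year × 100). It shows a spurious excess of about 6% in the arm that stops more (26.3/24.7 = 1.06). Under the constant hazard of step 3, the 39-week percentage is 14.8% in both arms.

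**6. Masking of a true excess.** Assume a hazard ratio of 1.25, control 87-week risk of 40%, and 40% v 10% stopping after one dose.

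- Control: 0.9 × 40.0 + 0.1 × 20.5 = 38.0%.
- Active: 0.6 × 47.2 + 0.4 × 24.9 = 38.3%.
- With equal 87-week follow-up the excess is 47.2 − 40.0 = 7.2 points.

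**7. Chance variation.** With about 60 per arm, the standard error of a difference is √(2p(1−p)/60): about 8.1 points near p = 27% and 9.1 points near p = 55%. The artefacts in step 3 are 2.2 and 3.7 points.

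**8. Collection limit against the visit schedule.** For last doses at Weeks 0, 4, 8 or 12 the limit falls at Weeks 39, 43, 47 or 51, before the Week 52 visit that Protocol 5.6 still asks for. If discontinuation is dated at the next missed dose, each limit moves four weeks later. Protocol 4.1 also allows ±7 days around the visit, so Week 12 is a borderline case.

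**The case against.** Several points on the other side stand.

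- **The drug's own toxicity would hide itself.** A reader might infer that if elezanumab causes events that stop dosing, its overall percentages fall. The tables do not support that. A subject who stops because of an event is already counted in the any-event row and has a dedicated row for events leading to discontinuation. First-infusion reactions occur inside every window. What remains is narrower: serious events, deaths, recurrent stroke, specific preferred terms and other later events.
- **Events after Week 39 are lost.** This is also too strong. Protocol 3.4, Protocol 6.1 and SAP 3.4 speak of monitoring throughout the study, SAP 9.2.1 sets no end date, and the all-deaths row has no treatment-emergent limit. The visit-level procedures are in appendices not in the supplied text. The documents show a conflict to settle, not a proven gap.
- **A rate per patient-year cures it.** Only if the hazard is roughly constant. Step 5 shows it can err in the opposite direction, and events concentrated soon after an acute stroke are plausible.
- **It matters little here.** Safety is descriptive, the trial is exploratory, and SAP sections 5.0 and 6.0 will show discontinuation and exposure by arm, so a reader could see an imbalance. Those tables do not show how far each event row was affected. The absence of tests does not remove a systematic distortion from the displayed percentages.

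Also, 39 weeks is not the realised minimum. Death, or study withdrawal with only an attempted 30-day call, gives less.

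**Conclusion.** The point holds in a limited form. The observation window moves with the end of dosing and the SAP reports only crude percentages. If early stopping is unequal, later events are understated in the arm that stops more.

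Under the assumed 35% v 15% split and identical hazards, the artefact is 2.2 points at 30% risk and 3.7 points at 60% risk with a constant hazard. It is 0.7 points at 30% risk when events come early. With equal stopping it disappears, and which arm would stop more cannot be known in advance. The size rests on assumed stopping shares and hazard shapes, and on stopping being unrelated to later event risk. In these illustrations it lies below chance variation. It is worth correcting because it is systematic, could mask a real excess when stopping is very unequal (step 6), and is cheap to remove.

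**What to change.** 1. **SAP 9.2.2 to 9.2.4.** Keep the crude percentages. For the main overview categories, serious events, deaths, events of special interest and recurrent stroke, add at least one summary that is robust to unequal follow-up:
   - time-to-first-event cumulative incidence by arm, censored at each subject's actual end of adverse-event observation, with death as a competing event for non-fatal events; and/or
   - percentages in a common window such as the first 39 weeks, with the number of subjects not observed for the whole window.

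   Both assume that stopping is unrelated to later event risk; state this.
2. **Exposure-adjusted rates** may be shown as well, using actual observation time rather than the treatment duration in SAP section 6.0, but not alone.
3. **Reconcile the recording period.** Bring the 39-week limit in Protocol 6.1 into line with Protocol 3.4, Protocol 5.6, the monitoring statement in 6.1 and SAP 3.4. Events found at study visits attended after that limit should be recorded and counted. State whether the clock starts at the last dose or at the decision to discontinue.

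Cost: one additional table set from dates already recorded, a wording change in the protocol, and adverse-event recording at visits already planned.

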9.2.3 Treatment-Emergent Adverse Events by SOC and PT

Treatment-emergent adverse events and corresponding subject numbers will be summarized by SOC and PT; by maximum relationship to study drug as assessed by the investigator (e.g., reasonable possibility or no reasonable possibility) and SOC and PT; by maximum severity and SOC and PT; and by subject number and SOC and PT. Specific adverse events will be counted once for each subject for calculating percentages, unless stated otherwise. In addition, if the same adverse event occurs multiple times within a subject, the highest severity and level of relationship to investigational product will be reported.

In addition, treatment-emergent adverse events will be summarized by PT and sorted by decreasing frequency for the elezanumab group.

Recurrent stroke events based on the embolic and thrombotic events SMQ provided in [Appendix B](#) will be tabulated and listed.

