2.3 Treatment Assignment and Blinding

Subjects will be randomized to elezanumab or placebo in a 1:1 ratio. Randomization will be stratified by intravenous (IV) tissue plasminogen activator (tPA) use (yes/no), treatment with endovascular therapy (EVT) (yes/no), and by time since "last known normal" (\leq 11 hours or $>$ 11) at the time of randomization.

The primary analysis of efficacy endpoints will be performed after the last subject completes the Week 52/Premature discontinuation visit. At this time, an interim database lock will occur, the randomization will be loaded into the database and the Data and Statistical Sciences department at AbbVie will perform the statistical analysis. Final safety analyses and post-treatment efficacy analyses will be performed following completion of the post-treatment period and database lock.

Study sites and subjects will remain blinded through the duration of the study.

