9.2.5 Adverse Events of Special Interest

Treatment-emergent adverse events of special interest will be summarized by SOC and PT and by maximum severity and will be based on standardized MedDRA queries (SMQs) or company MedDRA queries (CMQs). Infusion reactions are considered to be adverse events of special interest for elezanumab and will be display by each category provided in [Appendix B](#).

Detailed information about the search criteria is provided in [Appendix B](#).

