Appendix B. Definition of Adverse Events of Special Interest and Recurrent Stroke Events

Adverse Events of Special Interest (AESI) and recurrent stroke events will be identified using the following search criteria:

Area of Safety Interest	Search Criteria		
	Type	Name	Code
Infusion reactions	CMQ	Drug-induced rash	10000050
	SMQ	Hypersensitivity	20000214
	SMQ	Angiodema	20000024
	SMQ	Anaphylactic reaction	20000021
	CMQ	Injection site reaction	10000091
Recurrent stroke events	Type	Name	Code
	SMQ	Embolic and thrombotic events	20000081
	SMQ	Embolic and thrombotic events, arterial	20000082
	SMQ	Embolic and thrombotic events, venous	20000084
	SMQ	Embolic and thrombotic events, vessel type unspecified and mixed arterial and venous	20000083

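### SAP Appendix B identifies recurrent stroke by the whole embolic and thrombotic SMQ, venous events included, with no restriction to cerebrovascular terms and no stated selection step

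*SAP*

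**What the plan says.** SAP 9.2.3 announces one output on this topic: "Recurrent stroke events based on the embolic and thrombotic events SMQ provided in" Appendix B are to be tabulated and listed. Appendix B is titled "Definition of Adverse Events of Special Interest and Recurrent Stroke Events", and its opening sentence says that "recurrent stroke events will be identified using the following search criteria".

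Four searches stand under recurrent stroke: the overall embolic and thrombotic SMQ (20000081), "Embolic and thrombotic events, arterial" (20000082), "Embolic and thrombotic events, venous" (20000084), and the query for unspecified or mixed vessel type (20000083).

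For infusion reactions, which the same appendix covers, SAP 9.2.5 gives a layout: they "will be display by each category provided in" Appendix B. Neither 9.2.3 nor the appendix gives a layout for recurrent stroke.

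**The concern.** The label is narrower than the search. A reader of a table headed recurrent stroke will take it to count new strokes, but the rule as written admits any embolic or thrombotic event. In a trial of acute ischemic stroke, new strokes are an event that readers of the safety results will look for by arm, and the sponsor has given them their own output. If clots elsewhere in the body are mixed in, the comparison between arms can be diluted or misread in either direction.

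If the SMQ is meant only as a net from which strokes are then picked, the picking rule is unwritten. SAP 2.3 says that after the last Week 52 visit "an interim database lock will occur, the randomization will be loaded into the database", and that the final safety analyses follow a later lock. An unstated selection could therefore be made when treatment codes are already available. Nothing in the SAP says that it would be made that way, but nothing rules it out.

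**Working it through.** This is mainly a text check; the plan states no figure to reproduce.

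**1. What identifies a recurrent stroke event.** The only identification rule in the visible text is the Appendix B search.

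| Row under recurrent stroke | Code | Limited to cerebrovascular terms? |
|---|---|---|
| Overall query | 20000081 | No |
| Arterial | 20000082 | No |
| Venous | 20000084 | No |
| Unspecified or mixed vessel type | 20000083 | No |

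None of the four rows carries a restriction to the brain, and one is explicitly venous. Protocol 5.1 requires an index infarct in the anterior circulation, so the search is much wider than a recurrence of the index condition.

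**2. Whether another definition exists.** The AESI list in Protocol 6.1 contains only infusion reactions and does not define recurrent stroke. No preferred-term subset, adjudication or medical-review step for recurrent stroke appears in the visible protocol or SAP.

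**3. What the rule does to a non-stroke clot.** Take a subject whose only event is a venous clot outside the brain.
- Pooled display: the subject is counted as a recurrent stroke.
- Display by query: the venous row shows the event as venous, but the overall row still counts the subject under the recurrent-stroke heading.
- Retrieval net: the subject would be removed by a rule that is not written down.

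**4. Whether strokes can be counted from other outputs.** SAP 9.2.3 summarizes events by SOC and PT and "by subject number and SOC and PT". Each specific event counts once per subject, so adding several stroke rows can count one subject twice. The subject-number output allows a correct count by hand, but the reader must choose which terms are strokes.

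**5. Scale.** Protocol 4.2 plans about 120 subjects at 1:1.
- Per arm: 120 / 2 = 60.
- Weight of one subject: 1/60 = 0.0167, or 1.7 percentage points.
- If 50 per arm are dosed (assumed): 1/50 = 0.020, or 2.0 percentage points.

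These are weights per subject. No event rate is assumed, because the documents give none.

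**The case against.** The strongest reply is that this is a labelling matter in a minor output. Recurrent stroke is not a named safety endpoint (SAP 3.4), a row of the adverse event overview (SAP 9.2.2) or an AESI (SAP 9.2.5), and Protocol 7.4 rules out hypothesis tests on safety. True strokes can be read from the preferred-term tables, the subject-number output, the serious-event summaries in SAP 9.2.4 and the listing itself. All of that stands and limits the weight of the point.

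A second reply is that 9.2.3 concerns tables by SOC and PT, and that Appendix B lists the vessel types separately, so a layout that separates venous events is likely. That is plausible but not stated, and the overall row would still carry the wrong label.

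A third reply is that a broad search is this appendix's convention and was meant as retrieval only. The wording of 9.2.3 leaves some room for that. The appendix, however, calls itself a definition and says that the events are identified by these searches. If retrieval was meant, the selection rule is missing.

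It is also fair to say that 1.7 points is the weight of one subject in any table of this trial, and that the blinding risk is conditional. Both give context and do not show that an error has occurred. Finally, the Operations Manual and the DMC charter were not available and parts of the SAP are blacked out, so the absence of a selection step is established for the visible text only.

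**Conclusion.** The point holds. As written, the rule puts non-stroke clots into an output titled recurrent stroke; on the retrieval reading, it leaves the choice of strokes unwritten. Either way, a pre-specified count of recurrent strokes by arm is missing.

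The consequence is limited to one descriptive safety output. The primary NIHSS and secondary mRS analyses are untouched. The per-subject weight of 1.7 to 2.0 percentage points assumes 60 to 50 dosed subjects per arm. The number of subjects affected cannot be estimated. The preferred terms inside each query are not in the documents either, so the breadth of the search is read from the row names. It should be corrected, but it does not threaten the trial's conclusions on efficacy.

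**What to change.** Make these changes before the interim lock described in SAP 2.3, while the randomization is not yet loaded:

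- In Appendix B, define recurrent stroke by a pre-specified list of cerebrovascular preferred terms or by a stroke-specific query. State whether haemorrhagic stroke is included, since a count by arm cannot be interpreted without that.
- In 9.2.3, report the number and percentage of subjects by arm on that definition.
- Keep the present SMQ search as a separate table labelled as embolic and thrombotic events.
- If the SMQ is meant only as a retrieval net, write down the selection step and say that it is done blinded to treatment.

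The cost is one wording change in Appendix B, the matching line in 9.2.3 and one extra table from adverse event data already coded. No new data are needed.
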